## **3. PATIENT ACCOUNTING AND DISPOSITION**

### **3.1. Patient Accounting**

For each study site, the number of patients entered and randomized (overall and by treatment sequence) will be presented. The date of the first patient visit and the last patient visit for each study site will also be provided. These dates and patient totals will also be summarized for the whole study and by country.

A list of protocol deviations that could potentially impact the analysis of the study will be determined during the conduct of the study by study team members who are blinded to assigned study treatment. The number and percentage of patients with each deviation will be tabulated overall and by treatment using the Evaluable Population.

### **3.2. Patient Disposition**

The disposition of patients in the Evaluable Population will be presented separately. The summaries will include the number of patients randomized and randomized but not treated, as well as the number of patients treated in each treatment phase. The number of patients completing the study will be presented. For patients who do not complete the study, the reasons for study discontinuation as well as the study stage of discontinuation (i.e. Placebo Lead-in Phase 1, Treatment Phase 1, Washout, Placebo Lead-in Phase 2, Treatment Phase 2, and Follow-up) will be tabulated.

## **4. BASELINE CHARACTERISTICS**

Demographic data, baseline body measurements, and medical history will be summarized using descriptive statistics. Patients who are missing measurements of the baseline variable being analyzed will not be included in the summary for that variable.

### **4.1. Demographics**

Year of birth, gender, race, and ethnicity are collected during screening. As only the year of birth was collected, the patient's birthday will be approximated assuming the date as 1 July. Age at study entry will be based on the age of the patient on the date the informed consent is signed. Age at study entry will be analyzed as a continuous variable. Sex will be analyzed as a categorical variable. Patient race will be captured using multiple racial categories (i.e. American Indian or Alaskan Native, Asian, Black or African American, Native Hawaiian or other Pacific Islander, White, and Unwilling to provide). Patients selecting more than one race category will be tabulated using the category Multiple. The response for ethnicity could be Hispanic or Latino, Non-Hispanic or Non-Latino, or Unwilling to provide. Ethnicity will be analyzed as a categorical variable.

### **4.2. Baseline Anthropometrics**

The body measurements height, weight, body mass index (BMI), waist circumference, and percent fat mass will be recorded at baseline. Each will be reported as a continuous variable.

### **4.3. Medical History**

The number and percent of patients reporting relevant medical history will be presented at the system organ class (SOC) and preferred term (PT) levels.

## **5. CONCOMITANT MEDICATIONS**

Concomitant medications will be defined as medications taken during either treatment phase reporting period. This includes medications for which the start date is during a treatment phase reporting period, or for which the start date is before the date of the first dose of double-blind study drug but the end date is either during the treatment phase reporting period, after the end of the treatment phase reporting period, or for which the medication is on-going. Those medications where the stop date is documented as prior to the date of the first dose of double-blind study drug during the first treatment phase will be classified as prior medications.

## **6. EFFICACY ANALYSES**

Efficacy analyses for this study will be based on the findings from two instruments. First, the HQ-CT is a validated tool developed specifically for PWS to capture observations of problematic behaviors related to food. It consists of 9 items, with a 2-week recall period. The scale provides a composite value from 9 questions, each rated on a scale of 0 to 4 units (total range of score of 0 to 36; Fehnel et al. 2015).

Second, the CGIC is a single-item question rated on a 0 to 7 scale directed at the caregiver asking for an assessment of the overall improvement of patients with PWS.

Both of these assessments will be collected longitudinally during the study.

All efficacy analyses will be performed using the Evaluable Population. The method of analysis or statistical technique employed to address missing data will be described separately for each variable. Presentations of efficacy will include the number of patients with data at each time point plus related statistics derived from the analysis.

All statistical tests will be 1-sided.

## **6.1. Primary Efficacy Analysis**

The primary efficacy analysis will examine the contrast between GLWL-01 and placebo for the post-treatment HQ-CT total score at the end of the double-blind treatment phase.

The primary analysis will be conducted using a restricted maximum likelihood-based, mixed-effect model repeated measures analysis. The model for the primary analysis will include the fixed, categorical effects of sequence, period, and treatment, as well as the continuous, fixed covariate of the baseline Treatment Phase 1 HQ-CT score minus the baseline Treatment Phase 2 HQ-CT score (diff) and the interaction of period-by-diff (Mehrotra, 2014).

An unstructured covariance matrix will be used to model the within-patient errors.

Satterthwaite's approximation will be used to estimate the denominator degrees of freedom. The significance of differences in least-square means will be based on Type III tests using the observed population margins. The analyses will be performed using the SAS procedure PROC MIXED.

The tabular output for these MMRM analyses will present the least squares means, standard errors, and 95% confidence intervals for each marginal main effect. Pairwise contrasts of the least squares means between GLWL-01 and Placebo will also be provided at each time point using LSMESTIMATE statements.

Descriptive statistics for the HQ-CT score and the within-treatment phase changes from baseline will be provided by treatment and time point.

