10.3. Statistical Analyses

10.3.1. General Statistical Considerations

Statistical analysis of this study will be the responsibility of GLWL Research Inc. or its designee.

Efficacy analyses will be conducted on the randomized analysis set. This set includes all data from all randomized patients receiving at least 1 dose of double-blind study drug. Patients will be included in the analysis if they have a postbaseline measurement for the parameter being analyzed. Safety analyses will be conducted on the randomized analysis set. Patients will be analyzed according to the study drug they actually received.

Data will be presented using summary tables by treatment, unless otherwise specified.

Continuous data will be summarized using the mean, standard deviation, median (for selected variables), minimum, and maximum. Categorical data will be summarized as frequency counts and percentages. Figures may be used to support the presentation of selected data.

All tests of treatment effects will be conducted at a 2-sided alpha level of 0.05, unless otherwise stated.

Baseline values will be defined as the last available value prior to receiving double-blind study drug for each double-blind treatment phase.

For the purposes of follow-up analyses, the first 2 weeks of the washout period will be the follow-up for the Treatment Period 1 double-blind treatment phase and the Follow-up Period will be the follow-up for the Treatment Period 2 double-blind treatment phase.

Details related to handling of missing data will be described in the statistical analysis plan (SAP).

Any change to the data analysis methods described in the protocol will require an amendment only if it changes a principal feature of the protocol. Any other change to the data analysis

methods described in the protocol, and the justification for making the change, will be described in the SAP and/or in the clinical study report (CSR).

Additional exploratory analyses of the data will be conducted as deemed appropriate.

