10.3.3. Efficacy Analyses

10.3.3.1. Primary Analyses

The primary analysis will be conducted using a restricted maximum likelihood-based, mixed-effect model repeated measures analysis. The analysis of the primary endpoint will be the contrast between GLWL-01 and placebo at the end of the double-blind treatment phase on the posttreatment HQ-CT score.

The model for the primary analysis will include the fixed, categorical effects of sequence, period, and treatment, as well as the continuous, fixed covariate of the baseline double-blind Treatment Period 1 phase HQ-CT score minus the baseline double-blind Treatment Period 2 phase HQ-CT score (diff) and the interaction of period*diff (Mehrotra 2014).

An unstructured covariance structure will be used to model the within-patient errors.

Sensitivity analyses will be outlined in the SAP.

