## **2.3. Definition of Study Time Points**

For the summarization of demographic and background characteristics, the value of an endpoint will be the last measurement taken prior to the first dose of double-blind study drug during Treatment Period 1 on Study Day 14.

Baseline values will be determined separately for each treatment phase. The baseline values for each double-blind treatment phase will include the last measurements taken prior to or on the date of the first dose of the double-blind study drug, on Study Day 14 and Study Day 84, unless the time of the assessment/event was after the time the dose was administered. Treatment phase day will be defined separately for each treatment phase as

Treatment phase day = Visit Date – Date of 1st dose of double-blind study drug.

Therefore, Study Day 14 and Study Day 84 will be considered Treatment Phase Day 0 (i.e. Baseline) for Treatment Phase 1 and Treatment Phase 2, respectively. Similarly, Study Day 42 and Study Day 112 will be considered Treatment Phase Day 28 for Treatment Phase 1 and Treatment Phase 2, respectively.

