### **7.4. Vital Signs**

The vital signs pulse, temperature, and the mean (from triplicate measurements) sitting blood pressure will be assessed during screening; on Treatment Phase Day 0 (i.e. Baseline), Treatment Phase Day 7, and Treatment Phase Day 28 of each treatment phase; and at a patient's early termination visit, if applicable.

The number and percent of patients with any post-baseline pulse rate or mean blood pressure of potential clinical interest (including unscheduled and early termination assessments) will be summarized. Readings of potential clinical interest will be determined using the following criteria:

- Pulse rate either  $< 50$  bpm, or  $> 100$  bpm, or a change of  $\geq 15$  bpm;
- Systolic blood pressure either  $\leq 90$  mmHg, or  $\geq 160$  mmHg, or a change of  $\geq 20$  mmHg;
- Diastolic blood pressure either  $\leq 50$  mmHg, or  $\geq 100$  mmHg, or a change of  $\geq 10$  mmHg.

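### Does the promise of treatment contrasts at each time point in SAP 6.1 undermine a primary model that has no visit term?

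*SAP*

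**What the plan says.** SAP 6.1 defines the primary analysis as the "contrast between GLWL-01 and placebo for the post-treatment HQ-CT total score at the end of the double-blind treatment phase". Protocol 10.3.3.1 agrees: "contrast between GLWL-01 and placebo at the end of the double-blind treatment phase on the posttreatment HQ-CT score". SAP 2.3 gives the timing: "Study Day 42 and Study Day 112 will be considered Treatment Phase Day 28".

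On the model, SAP 6.1 says: "The model for the primary analysis will include the fixed, categorical effects of sequence, period, and treatment". It adds the Period 1 minus Period 2 baseline difference (diff), period-by-diff and an unstructured within-patient covariance. Protocol 10.3.3.1 lists the same terms. Neither document lists visit, or any interaction with visit.

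After describing the main output of these models, SAP 6.1 continues: "Pairwise contrasts of the least squares means between GLWL-01 and Placebo will also be provided at each time point using LSMESTIMATE statements". The next sentence reads: "Descriptive statistics for the HQ-CT score and the within-treatment phase changes from baseline will be provided by treatment and time point".

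SAP 2.3 maps only the baseline and Day 28 of each phase. A Day 7 visit appears in the SAP only in the safety sections; vital signs, for example, are taken on "Treatment Phase Day 7, and Treatment Phase Day 28 of each treatment phase". The protocol's Schedule of Activities also has HQ-CT at that visit.

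**The concern.** An LSMESTIMATE statement can only combine effects that are in the fitted model. With one treatment effect and no visit effect, it cannot return one contrast for Day 7 and another for Day 28. Either the model lacks terms or the output sentence promises something that the model cannot deliver.

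The worry is less the extra table than what a programmer might do to produce it. Adding Day 7 records to the primary dataset while keeping the listed terms would make the treatment coefficient an average over visits. The reported primary estimate would then no longer be the end-of-phase effect. With a 2-week recall on the HQ-CT, a weaker effect at Day 7 is plausible, so the blend could understate the Day 28 effect.

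**Working it through.** No figure in the plan bears on this point; the sample-size and power statements do not enter. The check is one of model structure, with a simulation for size.

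**Which visits are in play.** The double-blind phases start on Study Days 14 and 84. The Schedule of Activities has HQ-CT at Visits 4 and 9 (Days 21 and 91) and at Visits 5 and 10 (Days 42 and 112).

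- 21 − 14 = 91 − 84 = 7
- 42 − 14 = 112 − 84 = 28

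Each phase therefore has two post-baseline scores, at Day 7 and Day 28. Visit 6 (Day 56) falls 56 − 42 = 14 days after the first phase. Protocol 10.3.1 puts it in follow-up: "the first 2 weeks of the washout period will be the follow-up for the Treatment Period 1 double-blind treatment phase".

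**What one fit gives.** The columns are intercept, sequence, period, treatment, diff and period-by-diff: 6 in all. With the 19 patients anticipated in SAP 2.9:

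- Day 28 only: 2 × 19 = 38 records, 6 columns, rank 6.
- Days 7 and 28: 4 × 19 = 76 records, still 6 columns, rank 6.

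Within a phase the treatment column has the same value at both visits, so there is one treatment coefficient and no contrast that varies by visit.

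**Could a time point mean a period?** The algebra does not exclude it. Intercept, sequence, period and treatment are 4 parameters for the 4 sequence-by-period cells. Let τ be the treatment effect and λ the difference between the GLWL-01/placebo and placebo/GLWL-01 sequences. GLWL-01 minus placebo is then τ + λ in Period 1 and τ − λ in Period 2, and both are estimable. With simulated effects of −1 and −5, one fit returned −1.04 and −4.98. Their mean, (−1.04 − 4.98)/2 = −3.01, is the treatment coefficient. These per-period contrasts are confounded with sequence. It is the wording of the following sentence in SAP 6.1, which speaks of changes within a treatment phase, that points to visits instead.

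**Which records the primary fit uses.** Four things point to one Day 28 score per period:

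- Both documents place the primary contrast at the end of the phase.
- The paper cited for the model concerns, by its title, two-by-two crossovers with baselines.
- SAP 6.2.1 applies the same methods to the last HQ-CT observation in each phase, which is one value per phase.
- SAP 8 applies them to AG and UAG, which the schedule draws once after baseline in each phase.

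The listed terms must therefore work as a two-record model. Its unstructured covariance is 2×2, with 2 × 3/2 = 3 parameters.

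**Size if the visits were stacked instead.** The assumptions, none of them in the documents, are SD 4, within-phase correlation 0.6, between-phase correlation 0.5 and a true Day 28 effect of −3. The entries are mean estimates over 200 simulated trials of 19 patients.

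| True Day 7 effect | Day 28 records only | Both visits, listed terms only | Every term by visit: Day 7 / Day 28 |
|---|---|---|---|
| −3 | −3.04 | −3.07 | −3.05 / −3.04 |
| −1.5 | −3.05 | −2.33 | −1.55 / −3.05 |
| 0 | −3.03 | −1.52 | 0.03 / −3.03 |

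Separate fits to the Day 7 records gave −3.05, −1.55 and 0.03, the same as the fully interacted model. With complete data, the two sensible ways of producing the table agree and both leave the Day 28 contrast where it was. Only stacking without visit terms moves it.

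**What a Day 7 contrast would mean.** A 14-day recall at Day 7 reaches 14 − 7 = 7 days before the first double-blind dose. About half the window is untreated, so the contrast is descriptive at best.

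**The case for a change.** The strongest case for a change is that the SAP never says only end-of-phase records enter the primary fit. SAP 2.4 gives MMRM the job of limiting the impact of missing data, SAP 6 says HQ-CT is collected longitudinally, and the disputed sentence describes output from the same models. A literal programmer could stack the visits, and the table shows this would matter. Two sentences in SAP 6.1 and a line in SAP 2.3 would settle it at almost no cost.

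Part of this stands. The primary result is safe only on the two-record reading, which the text indicates but does not state. The visits for the extra contrasts are also not named in SAP 2.3.

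The rest carries less weight. Stacking with the listed terms yields neither the by-visit contrasts nor the end-of-phase contrast, so it fails both things SAP 6.1 asks for. The failure shows as soon as someone writes the LSMESTIMATE statement and finds no visit effect to use. SAP 2 also requires independent programming and a senior statistical review against the plan. The missing-data role of the mixed model is partly met with two records: a patient with both baselines but one end-of-phase score still contributes. Table layouts sit in a companion document (SAP 1.1), which was not available here and may name the visits.

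**Conclusion.** The mismatch is real but amounts to missing detail about a supplementary table. The primary contrast is fixed at Day 28 in both documents. If the fit uses one end-of-phase score per period, as the wording indicates, the primary estimate, its standard error and its test do not change. The output left open is one extra time point (Day 7), or two if the post-phase assessment is counted, for the HQ-CT total and the two-item severity measure, and possibly Day 7 for total cholesterol and glucose. SAP 2.6 names a single primary endpoint, and nothing in the SAP ties a decision to these extra contrasts. An analyst would produce them by refitting the model at each visit or by interacting every term with visit; on complete data the two give the same answers.

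The conclusion rests on the two-record reading. The blended values in the table depend on the assumed SD, correlations and Day 7 effect. That one fit of the listed terms gives no visit-specific contrast does not depend on them.

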### **6.1.1. Sensitivity Analyses for the Primary Efficacy Variable**

Sensitivity analyses of the primary endpoint may be performed if the primary efficacy analysis demonstrates a difference between GLWL-01 and placebo. These contingent analyses will be detailed in an addendum to this SAP.

## **6.2. Secondary Efficacy Analyses**

### **6.2.1. Additional analyses from the HQ-CT**

The last observation of the HQ-CT in the treatment phase will be separately analyzed using the same methods used for the primary efficacy endpoint. Similarly, the sixth and ninth items of the HQ-CT comprise a measure of the severity of hyperphagia, which will be analyzed using the same methods.

## **6.2.2. Analyses of the Caregiver Global Impression of Change**

The CGIC will be analyzed using similar methods used for the primary efficacy endpoint. The analysis of the CGIC will also be conducted using MMRM. The model for the analysis will include the fixed, categorical effects of sequence, period, and treatment.

## **7. SAFETY ANALYSES**

All summaries of safety, including the extent of exposure to study medication, will be performed using the Evaluable Population. No statistical analyses are planned on safety endpoints.

### **7.1. Study Medication Exposure and Treatment Compliance**

#### **7.1.1. Extent of Exposure**

Time on study will be derived for each patient as:

Time on study = Date of last dose of study drug – Date of 1st dose from lead-in phase 1 + 1.

The extent of exposure to double-blind study drug will be derived for each treatment phase as:

Extent of exposure = Date of last dose of double-blind study drug - Date of 1st dose of double-blind study drug + 1.

Time on study and extent of exposure will be descriptively summarized for each treatment sequence and treatment arm.

#### **7.1.2. Treatment Compliance**

Treatment compliance will be calculated for each treatment phase using the formula:

$$\text{Treatment Compliance} = 100 \left( \frac{\text{number of capsules received}}{\text{number of capsules intended}} \right).$$

The total number of tablets intended is equal to 6 times the number of days the patient spent in each treatment phase.

Treatment compliance will be descriptively summarized for each treatment arm. In addition, the number and percent of patients with compliance < 80% or > 120% will also be presented for each treatment arm.

## **7.2. Adverse Events**

Adverse events (AEs) will be collected from the day the patient gives informed consent until the patient leaves the study. However, if the investigator learns of any serious adverse event (SAE) that occurs within 30 days after the final dose of study drug, that SAE will be collected even if the event occurred after the patient left the study.

TEAEs for each treatment phase reporting period are defined as reported AEs that first occurred or worsened after the first dose of double-blind study drug. Adverse events with an onset date on or after the first dose of double-blind study drug for Period 1 and before the first dose of double-blind study drug for Period 2 will be assigned to the study drug taken during Period 1; adverse

events with an onset date on or after the first dose of double-blind study drug for Period 2 will be assigned to the study drug taken during Period 2.

Treatment-emergent adverse events will be summarized by the number and percent of patients with the event.

Summaries of TEAEs will include the number of patients with at least one TEAE for each treatment arm. When reporting by system organ class (SOC) and preferred term (PT), the reports will present the SOC in alphabetical order; while PTs within the SOC will be presented in order of overall decreasing frequency of occurrence in the GLWL-01 arm. A patient with multiple TEAEs (different PTs) coded to the same SOC will be counted only once for that SOC, but will be counted each time for different PTs within that SOC. A patient with separate events of the same PT (different start/stop dates within a treatment phase) will be counted only once in the frequency tables for that PT.

An overview of all TEAEs will also be provided by treatment group using the types of AEs defined in the following subsections.

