### **2.3.1. Reporting Periods for Concomitant Medications and Safety Endpoints**

For adverse events and concomitant medications, and for unscheduled safety assessments (e.g. laboratory measurements), the reporting period for each treatment phase will include all data recorded after the first dose of double-blind study drug up to 14 days after the last dose of double-blind study drug.

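### SAP 7.2 allows two adverse-event windows: 42 days by its TEAE definition, but 70 days in Period 1, with no stated end in Period 2, by its assignment sentence

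*SAP*

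**What the plan says.** SAP 7.2 opens its definition with the words "TEAEs for each treatment phase reporting period are defined as reported AEs that first occurred or worsened", counted after the first double-blind dose. The term reporting period comes from SAP 2.3.1, which applies it expressly to adverse events and runs it from the first double-blind dose "up to 14 days after the last dose of double-blind study drug". SAP 5 uses the same term for medications: "Concomitant medications will be defined as medications taken during either treatment phase reporting period".

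SAP 7.2 then allocates events to drugs. Those with onset from the first Period 1 dose and "before the first dose of double-blind study drug for Period 2 will be assigned to the study drug taken during Period 1"; and "events with an onset date on or after the first dose of double-blind study drug for Period 2 will be assigned" to the Period 2 drug. No end is given for Period 2.

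On collection, SAP 7.2 says that adverse events "will be collected from the day the patient gives informed consent until the patient leaves the study". For a serious event within 30 days of the final dose, it adds "that SAE will be collected even if the event occurred after the patient left the study". TEAEs "will be summarized by the number and percent of patients with the event".

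The protocol has one window. Section 10.3.4 counts the double-blind phase plus follow-up, and section 10.3.1 sets follow-up for Period 1 as the first two weeks of washout and for Period 2 as the Follow-up Period. SAP 2.9 records a change in how TEAEs are determined, but the reason given is the way worsening events are recorded. It mentions no change of window.

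**The concern.** The definition and the assignment sentence imply different windows, and nothing makes the second subject to the first. Two programmers working from SAP 7.2 could therefore produce different TEAE tables.

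Under the wider reading, Period 1 gains the last 14 days of washout and the 14-day second lead-in, when every patient takes placebo. Events starting then are credited to the Period 1 drug. In the GLWL-01/placebo sequence they would appear as GLWL-01 events although they began off drug or on lead-in placebo. The same rule feeds the related, serious, discontinuation and severity tables in SAP 7.2.2 to 7.2.6. The two periods would also have unequal time at risk. For a patient who never starts Period 2, the Period 1 assignment would have no end date at all.

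TEAEs are the endpoint of a secondary objective, so the window should be fixed before treatment codes are known.

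**Working it through.** **Inputs from the documents.** First double-blind doses are on Days 14 and 84, and Phase Day 28 falls on Days 42 and 112 (SAP 2.3). The reporting period ends 14 days after the last dose (SAP 2.3.1). The follow-up visit is on Day 126 (protocol Schedule of Activities). Serious events are collected to 30 days after the last dose (SAP 7.2, protocol 9.2.1). Nineteen patients are anticipated (SAP 2.9).

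**The plan's own figure.** 42 − 14 = 28 and 112 − 84 = 28, as SAP 2.3 states.

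**Windows**
- Reporting period, each phase: 28 + 14 = 42 days (Day 14 to 56; Day 84 to 126). It is 41 days if the last Period 1 dose is on Day 41.
- Assignment window, Period 1: 84 − 14 = 70 days (66 to 74 with the ±2-day visit windows).
- Excess: 70 − 42 = 28 days, made up of 14 days of washout (Day 56 to 70) and 14 days of lead-in (Day 70 to 84).
- Period 2 in practice: 126 − 84 = 42 days for adverse events, because collection stops at study exit; up to 28 + 30 = 58 days for serious events.

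**Assumptions for size.** The documents give no event rate and no realised sequence split. I take all 19 patients as completers, with *a* on GLWL-01 first and *b* on placebo first, and a constant background rate.

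**At-risk days, GLWL-01 v placebo**
- 42-day reading: 19 × 42 = 798 in each column.
- Wider reading, all events: 70a + 42b v 70b + 42a. At 10:9, 1078 v 1050; at 12:7, 1134 v 994.
- Wider reading, serious events, at most: 70a + 58b v 70b + 58a. At 10:9, 1222 v 1210; at 12:7, 1246 v 1186.
- GLWL-01 days outside the SAP 2.3.1 period: 28a, so 280/1078 = 26% or 336/1134 = 30%.

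**Percent of patients with an event.** Let p1 and p0 be the 42-day incidences on GLWL-01 and placebo, and s = (1 − p0)^(28/42) the chance of no event in the extra 28 days.
- GLWL-01: [a(1 − (1 − p1)s) + b·p1]/19
- Placebo: [b(1 − (1 − p0)s) + a·p0]/19

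| p1, p0 | Split a:b | GLWL-01 | Placebo | Difference (points) | Ratio |
|---|---|---|---|---|---|
| 40%, 40% | 10:9 | 49.1% | 48.2% | 0.91 | |
| 40%, 40% | 12:7 | 50.9% | 46.4% | 4.56 | |
| 20%, 20% | 10:9 | 25.8% | 25.2% | 0.58 | |
| 20%, 20% | 12:7 | 27.0% | 24.1% | 2.91 | |
| 40%, 20% | 10:9 | 44.4% | 25.2% | 19.13 | 1.76 |
| 40%, 20% | 12:7 | 45.2% | 24.1% | 21.16 | 1.88 |
| 40%, 20% | 7:12 | 43.1% | 27.0% | 16.07 | 1.60 |

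One patient is 1/19 = 5.3 points. The two gaps at 40% with no drug effect are therefore 19 × 0.0091 = 0.17 patient and 19 × 0.0456 = 0.87 patient. In the last three rows the 42-day reading would give a difference of 20 points and a ratio of 2.00.

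**The case against.** The two sentences can be reconciled. The reporting period would decide what counts as a TEAE, and the assignment sentence would decide only which drug an event belongs to. An event on Day 65 would then be assigned to the Period 1 drug and still stay out of the TEAE tables. This is a natural reading: it fits the protocol and the silence of SAP 2.9 on any change of window. It is not stated, though, and if only reporting-period events counted, Period 1 would close around Day 56 and a boundary at the Period 2 first dose would do no work. Unseen table formats may settle the matter, but the SAP itself should.

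Several limits on the impact do stand:
- The extra 28 days attach to Period 1 rather than to a treatment, so placebo-first patients add events to the placebo column in the same way, and near-balanced sequences largely cancel.
- The open end of Period 2 hardly matters for non-serious events, since collection stops at about the day the reporting period ends. All serious events are listed anyway (SAP 7.2.3).
- No exposure-adjusted rate is planned, so the at-risk days describe the imbalance and enter no table.
- SAP 7 plans no statistical analysis of safety endpoints.
- The independent programming required by SAP 2 could expose a divergence, though possibly only after unblinding.

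**Conclusion.** The concern holds: SAP 7.2 contains two rules that give different windows, 42 and 70 days in Period 1, and does not say which prevails. The consequence is minor to moderate. With no true effect, the spurious gap stays below one patient at the splits tried. With a true effect, the risk difference can move either way (16.1 to 21.2 points against 20), while the risk ratio moves toward 1 in all three cases. The window lengths follow directly from the documents. The incidences, splits, completion by all 19 and constant background rate are assumptions. The case for correcting the text rests on having one reproducible TEAE table and on keeping events that began in late washout or on lead-in placebo out of the GLWL-01 column.

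**What to change.** Before unblinding, add a sentence to SAP 7.2 stating that TEAEs, and their assignment to a treatment, are limited to each phase's SAP 2.3.1 reporting period: from the first double-blind dose to 14 days after the last double-blind dose of that phase.

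Add a listing of all adverse events and serious adverse events that start after the first double-blind dose but outside those periods, that is, between the end of the Period 1 window and the first Period 2 dose, and after the Period 2 window. Show the study period of each event. Since serious events are already listed, this mainly adds the non-serious ones and keeps them visible.

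The cost is one sentence and one listing. Onset dates are already captured, so no new data are needed.
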